11.6 Reporting of Pregnancy

Pregnancy itself is not an AE. Pregnancies and complications of pregnancies will be reported as information items and in summary at the time of CR.

11.7 Type and Duration of the Follow-up of Subjects after Adverse Events

- The participant will be withdrawn from the study if the AE occurs before drug administration, at the discretion of the principal investigator.
- The study drug (both ATV and ASA) will be discontinued immediately if the AE occurs during the treatment phase at the discretion of the investigator. The participant will be followed as necessary throughout the remainder of the study period for safety assessments and labs.

11.8 Modification of Study Agent(s)/Intervention(s) for a Subject

If a participant is unable to tolerate ATV or ASA, they will discontinue study drug and will be withdrawn from study. No dose adjustment will occur during the course of this study. See 11.7 for AEs.

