N	Number (typically refers to number of subjects/sample size)
NIAID	National Institute of Allergy and Infectious Diseases
NIH	National Institutes of Health
NSAID	nonsteroidal anti-inflammatory drugs
OHRP	Office for Human Research Protections
PBMC	Peripheral Mononuclear Cells
PCR	Polymerase Chain Reaction
PI	Principal Investigator
RCHSPB	Regulatory Compliance and Human Subjects Protection Branch
RNA	Ribonucleic Acid
SAE	Serious Adverse Event
sTF	soluable tissue factor

SVR	Sustained virologic response
ULN	Upper Limit of Normal
UP	Unanticipated Problem
UPnonAE	Unanticipated Problem that is not an Adverse Event

PROTOCOL SUMMARY

Full Title:	Elite Controller and ART-treated HIV+ Statin versus ASA Treatment Intervention Study (ECSTATIN)
Short Title:	Immune Activation in Elite Controllers
Clinical Phase:	Phase 1
Protocol	14-I-0039
Conducted by:	NIAID-DIR
Principal Investigator:	[name].
Sample Size:	N=80 Elite Controller (EC) Group: N=40 Randomization arms: aspirin (ASA): N=20 atorvastatin (ATV): N=20 Treated Progressor Group (ART<50): N=40 Randomization arms: ASA: N=20 ATV: N=20
Accrual Ceiling:	N=120
Study Population:	Subjects (≥ 18 years) infected with the human immunodeficiency virus type 1 (HIV-1) grouped ECs (no opportunistic infections [OIs], no antiretroviral therapy [ART], stable CD4 T cell counts greater than 3 years, HIV-RNA less than the lower limit of detection (LLD) of commercially available assays) OR on continuous combination ART ≥ 4 years with HIV-RNA less than the lower limit of detection (LLD) of commercially available assays). Transient measurements of detectable viremia, or “blips,” are allowed, if flanked by viral loads less than the lower limit of detection.
Accrual Period:	4 Years
Study Design:	This is an open-label, randomized controlled trial intended to study potential modifiers of immune activation in HIV-1 infected ECs (no OIs, no ART, stable CD4 T cell counts greater than 3 years, viral load less than the LLD of the assay used) (EC group) and treated progressors on continuous combination ART for ≥ 4 years with HIV-RNA below the limit of detection in commercially available assays (<40, <48, or <50 copies/mL, depending on the assay used) for greater than 3 years (ART <50 group). After screening at

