5.3 Preparation, Administration, and Dosage of Study Agent/Intervention(s)

5.3.1 Study Agent : atorvastatin

Description

Dosing and Administration: 40 mg tablet, daily. In subjects on certain antiretroviral medications, ATV dosing will be adjusted in accordance with DHHS guidelines [84]. See Table 1 below for list of antiretroviral agents requiring adjustment. Briefly, in subjects on cobicistat -or ritonavir- boosted protease inhibitor or elvitegravir-based regimens, the atorvastatin AUC can increase by 3-6 fold [87]. In subjects on protease inhibitor (other than tipranavir) or elvitegravir-based regimens, the atorvastatin dose will be decreased to 20mg daily. In subjects on efavirenz or etravirine-based regimens, atorvastatin AUC can decrease from 32 to 43%. Therefore, in subjects on efavirenz or etravirine-based regimens, the dose of atorvastatin will be increased to 80mg daily. Dosing of ATV with other ART regimens will also be made in accordance with DHHS guidelines [84].

Table 1. Atorvastatin Interactions with Selected Antiretrovirals and Dosing Recommendations

Antiretroviral Medication	Effect on Atorvastatin	Adjusted Atorvastatin
Atazanavir, Atazanavir with Ritonavir or Cobicistat	Increased Atorvastatin possible	20mg,daily
Darunavir with Ritonavir or Cobicistat	DRV/r + Atorvastatin 10mg similar to Atorvastatin 40mg administered alone	20mg daily
Elvitegravir with Cobicistat (or Ritonavir)	Increased Atorvastatin possible	20mg, daily
Lopinavir with ritonavir	Increased AtorvastatinAUC 488%	20mg daily
Efavirenz, Etravirine	Decreased Atorvastatin AUC 32-43%	80mg daily
Rilpivirine	Atorvastatin AUC unchanged	40mg daily

Route of Administration: PO

Duration of Therapy: 9 months

Tracking of Dose: pill count and participant stated compliance.

Limitations on Prior Therapy: Prior statin therapy allowable if therapy ceased at least 6 months prior to the screening visit.

Subject Access to Study Agent at Study Closure: ATV is only available by prescription, and subjects will be counseled to consult with their primary physician before considering chronic therapy.

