7 DRUG INTERACTIONS

The risk of myopathy during treatment with statins is increased with concurrent administration of fibric acid derivatives, lipid-modifying doses of niacin, cyclosporine, or strong CYP 3A4 inhibitors (e.g., clarithromycin, HIV protease inhibitors, and itraconazole) [see *Warnings and Precautions, Skeletal Muscle* (5.1) and *Clinical Pharmacology* (12.3)].

7.1 Strong Inhibitors of CYP 3A4: Atorvastatin is metabolized by cytochrome P450 3A4. Concomitant administration of atorvastatin calcium tablets with strong inhibitors of CYP 3A4 can lead to increases in plasma concentrations of atorvastatin. The extent of interaction and potentiation of effects depend on the variability of effect on CYP 3A4.

Clarithromycin: Atorvastatin AUC was significantly increased with concomitant administration of atorvastatin calcium tablets 80 mg with clarithromycin (500 mg twice daily) compared to that of atorvastatin calcium tablets alone [see *Clinical Pharmacology* (12.3)]. Therefore, in patients taking clarithromycin, caution should be used when the atorvastatin dose exceeds 20 mg [see *Warnings and Precautions, Skeletal Muscle* (5.1) and *Dosage and Administration* (2.6)].

Combination of Protease Inhibitors: Atorvastatin AUC was significantly increased with concomitant administration of atorvastatin calcium tablets with several combinations of HIV protease inhibitors, as well as with the hepatitis C protease inhibitor telaprevir, compared to that of atorvastatin calcium tablets alone [see *Clinical Pharmacology* (12.3)]. Therefore, in patients taking the HIV protease inhibitor tipranavir plus ritonavir, or the hepatitis C protease inhibitor telaprevir, concomitant use of atorvastatin calcium tablets should be avoided. In patients taking the HIV protease inhibitor lopinavir plus ritonavir, caution should be used when prescribing atorvastatin calcium tablets and the lowest dose necessary should be used. In patients taking the HIV protease inhibitors saquinavir plus ritonavir, darunavir plus ritonavir, fosamprenavir, or fosamprenavir plus ritonavir, the dose of atorvastatin calcium tablets should not exceed 20 mg and should be used with caution [see *Warnings and Precautions, Skeletal Muscle* (5.1) and *Dosage and Administration* (2.6)]. In patients taking the HIV protease inhibitor nelfinavir or the hepatitis C protease inhibitor boceprevir, the dose of atorvastatin calcium tablets should not exceed 40 mg and close clinical monitoring is recommended.

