12.3 Pharmacokinetics

Absorption: Atorvastatin calcium tablets are rapidly absorbed after oral administration; maximum plasma concentrations occur within 1 to 2 hours. Extent of absorption increases in proportion to atorvastatin calcium dose. The absolute bioavailability of atorvastatin (parent drug) is approximately 14% and the systemic availability of HMG-CoA reductase inhibitory activity is approximately 30%. The low systemic availability is attributed to presystemic clearance in gastrointestinal mucosa and/or hepatic first-pass metabolism. Although food decreases the rate and extent of drug absorption by approximately 25% and 9%, respectively, as assessed by C_{max} and AUC, LDL-C reduction is similar whether atorvastatin calcium tablets are given with or without food. Plasma atorvastatin concentrations are lower (approximately 30% for C_{max} and AUC) following evening drug administration compared with morning. However, LDL-C reduction is the same regardless of the time of day of drug administration [see *Dosage and Administration (2)*].

Distribution: Mean volume of distribution of atorvastatin is approximately 381 liters. Atorvastatin is ≥98% bound to plasma proteins. A blood/plasma ratio of approximately 0.25 indicates poor drug penetration into red blood cells. Based on observations in rats, atorvastatin is likely to be secreted in human milk [see *Contraindications, Nursing Mothers (4.4)* and *Use in Specific Populations, Nursing Mothers (8.3)*].

Metabolism: Atorvastatin is extensively metabolized to ortho- and parahydroxylated derivatives and various beta-oxidation products. *In vitro* inhibition of HMG-CoA reductase by ortho- and parahydroxylated metabolites is equivalent to that of atorvastatin. Approximately 70% of circulating inhibitory activity for HMG-CoA reductase is attributed to active metabolites. *In vitro* studies suggest the importance of atorvastatin metabolism by cytochrome P450 3A4, consistent with increased plasma concentrations of atorvastatin in humans following co-administration with erythromycin, a known inhibitor of this isozyme [see *Drug Interactions (7.1)*]. In animals, the ortho-hydroxy metabolite undergoes further glucuronidation.

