[#] Tipranavir 500 mg BID/ritonavir 200 mg BID, 7 days	10 mg, SD	↑ 9.4 fold	↑ 8.6 fold
[#] Telaprevir 750 mg q8h, 10 days	20 mg, SD	↑ 7.88 fold	↑ 10.6 fold
^{#, †} Saquinavir 400 mg BID/ ritonavir 400 mg BID, 15 days	40 mg QD for 4 days	↑ 3.9 fold	↑ 4.3 fold
[#] Clarithromycin 500 mg BID, 9 days	80 mg QD for 8 days	↑ 4.4 fold	↑ 5.4 fold
[#] Darunavir 300 mg BID/ritonavir 100 mg BID, 9 days	10 mg QD for 4 days	↑ 3.4 fold	↑ 2.25 fold
[#] Itraconazole 200 mg QD, 4 days	40 mg SD	↑ 3.3 fold	↑ 20%
[#] Fosamprenavir 700 mg BID/ritonavir 100 mg BID, 14 days	10 mg QD for 4 days	↑ 2.53 fold	↑ 2.84 fold
[#] Fosamprenavir 1400 mg BID, 14 days	10 mg QD for 4 days	↑ 2.3 fold	↑ 4.04 fold
[#] Nelfinavir 1250 mg BID, 14 days	10 mg QD for 28 days	↑ 74%	↑ 2.2 fold
[#] Grapefruit Juice, 240 mL QD *	40 mg, SD	↑ 37%	↑ 16%
Diltiazem 240 mg QD, 28 days	40 mg, SD	↑ 51%	No change
Erythromycin 500 mg QID, 7 days	10 mg, SD	↑ 33%	↑ 38%
Amlodipine 10 mg, single dose	80 mg, SD	↑ 15%	↓ 12 %
Cimetidine 300 mg QD, 4 weeks	10 mg QD for 2 weeks	↓ Less than 1%	↓ 11%
Colestipol 10 mg BID, 28 weeks	40 mg QD for 28 weeks	Not determined	↓ 26%**
Maalox TC® 30 mL QD, 17 days	10 mg QD for 15 days	↓ 33%	↓ 34%
Efavirenz 600 mg QD, 14 days	10 mg for 3 days	↓ 41%	↓ 1%
[#] Rifampin 600 mg QD, 7 days (co-administered) [†]	40 mg SD	↑ 30%	↑ 2.7 fold
[#] Rifampin 600 mg QD, 5 days (doses separated) [†]	40 mg SD	↓ 80%	↓ 40%
[#] Gemfibrozil 600mg BID, 7 days	40mg SD	↑ 35%	↓ Less than 1%
[#] Fenofibrate 160mg QD, 7 days	40mg SD	↑ 3%	↑ 2%
Boceprevir 800 mg TID, 7 days	40 mg SD	↑2.30 fold	↑2.66 fold

[&] Data given as x-fold change represent a simple ratio between co-administration and atorvastatin alone (i.e., 1-fold = no change). Data given as % change represent % difference relative to atorvastatin alone (i.e., 0% = no change).

[#] See Sections 5.1 and 7 for clinical significance.

* Greater increases in AUC (up to 2.5 fold) and/or C_{max} (up to 71%) have been reported with excessive grapefruit consumption (≥ 750 mL - 1.2 liters per day).

** Single sample taken 8-16 h post dose.

[†] Due to the dual interaction mechanism of rifampin, simultaneous co-administration of atorvastatin with rifampin is recommended, as delayed administration of atorvastatin after administration of rifampin has been associated with a significant reduction in atorvastatin plasma concentrations.

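### Section 11.8 bars dose adjustment without limiting this to intolerance, so it conflicts with the regimen-based atorvastatin doses in 5.3.1 if a participant switches antiretrovirals after Month 3

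*Combined protocol and SAP*

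**What the plan says.** Section 5.3.1 ties the atorvastatin dose to the antiretroviral regimen. The standard dose is 40 mg, and Table 1 also gives 40 mg with rilpivirine. For inhibitors: "In subjects on protease inhibitor (other than tipranavir) or elvitegravir-based regimens, the atorvastatin dose will be decreased to 20mg daily". For efavirenz or etravirine, "the dose of atorvastatin will be increased to 80mg daily". For regimens not listed: "Dosing of ATV with other ART regimens will also be made in accordance with DHHS guidelines". The section does not say whether the dose is set once at Month 3 or follows the current regimen.

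Section 11.8 has a general heading on modifying study agents. Its first sentence says that a participant who cannot tolerate the drug stops it and is withdrawn. Its second is "No dose adjustment will occur during the course of this study". It ends by pointing to 11.7 for adverse events and does not mention 5.3.1.

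Section 5.7 and exclusion 8 prohibit only tipranavir and combinations of a non-nucleoside inhibitor with a protease inhibitor. The ART<50 inclusion criteria ask for more than 4 years of continuous therapy, not for an unchanged regimen. The planned allocation is "Treated Progressor Group (ART<50): N=40 Randomization arms: ASA: N=20 ATV: N=20".

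The atorvastatin label in Appendix D (7.1) says that with darunavir/ritonavir and certain other protease inhibitors "the dose of atorvastatin calcium tablets should not exceed 20 mg and should be used with caution".

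**The concern.** A participant may change from one permitted regimen to another in a different dose band during the 9 months of treatment. Section 5.3.1 then points to a new dose, while 11.8, read as written, keeps the old one. No section settles which applies.

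The conflict would arise at a definite moment. Appendix B has drug dispensed at Months 3, 6 and 9, and 6.5 has a medication history taken at Months 6 and 9. Staff would therefore usually learn of the switch at the visit where they must decide what to dispense.

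What is at stake is participant safety. Section 8.1 and Appendix D (5.1) both link higher atorvastatin doses taken with HIV protease inhibitors to myopathy and rhabdomyolysis. The participants concerned have no clinical indication for the drug.

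**Working it through.** The plan gives no figure on this point to reproduce. The check compares the rules, then sizes the consequence.

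**1. Dose after a switch if 11.8 is followed literally**

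| Switch | Dose kept | Table 1 dose | Ratio |
|---|---|---|---|
| Efavirenz or etravirine to protease inhibitor or elvitegravir | 80 mg | 20 mg | 80/20 = 4 |
| Rilpivirine or other 40 mg regimen to protease inhibitor or elvitegravir | 40 mg | 20 mg | 40/20 = 2 |

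For darunavir/ritonavir the Appendix D cap is also 20 mg, so the same ratios apply to the label limit.

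**2. Exposure (illustration)**

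Exposure in mg-equivalents = dose × AUC ratio. Inputs:
- Efavirenz: 1 − 0.41 = 0.59 (Appendix D, Table 3).
- Darunavir/ritonavir: 3.4 (Appendix D, Table 3, row "Darunavir 300 mg BID/ritonavir 100 mg BID, 9 days").
- Rilpivirine: 1.0 (protocol Table 1, AUC unchanged).

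Assumptions: AUC is proportional to dose (the label says "Extent of absorption increases in proportion to atorvastatin calcium dose"), and the efavirenz and darunavir/ritonavir ratios, both measured at 10 mg, hold at higher doses and for the participant's own regimen.

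At Table 1 doses: efavirenz 80 × 0.59 = 47.2; rilpivirine 40 × 1.0 = 40; darunavir/ritonavir 20 × 3.4 = 68.

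| Switch | Dose unchanged, relative to before | Re-dosed, relative to before |
|---|---|---|
| Efavirenz to darunavir/r | 80 × 3.4 = 272; 272/47.2 = 5.8 | 68/47.2 = 1.4 |
| Rilpivirine to darunavir/r | 40 × 3.4 = 136; 136/40 = 3.4 | 68/40 = 1.7 |
| Efavirenz to rilpivirine | 80/47.2 = 1.7 | 40/47.2 = 0.85 |

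The three reverse paths, dose unchanged, lower exposure: 20 × 0.59 = 11.8 and 11.8/68 = 0.17; 20/68 = 0.29; 40 × 0.59 = 23.6 and 23.6/40 = 0.59.

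The broader 3- to 6-fold range in 5.3.1 gives the same direction: 80 mg becomes 240 to 480 mg-equivalents, against 60 to 120 at 20 mg.

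**3. Duration due to 11.8**

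Drug stops at Month 12. A switch found at Month 6 would leave 12 − 6 = 6 more months at the old dose; one found at Month 9 would leave 12 − 9 = 3. Any delay before the visit, about 3 months at most, comes from the visit schedule and not from 11.8.

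**4. Number of participants**

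The group is mainly the 20 ART<50 participants on atorvastatin, 20/80 = 25% of the trial. Elite controllers enter off therapy and matter only if they start it on study. The documents give no switch rate. If a proportion p of the 20 crosses any dose band, the expected number is 20p and the chance of none is (1 − p)^20:

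| Assumed p | Expected | Chance of none |
|---|---|---|
| 2% | 0.4 | 67% |
| 5% | 1 | 36% |
| 10% | 2 | 12% |

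These counts include switches that lower exposure. At each assumed p, they are upper bounds on the number left above the Table 1 dose.

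**The case against.** The strongest reply is that 11.8 concerns tolerability only. The sentence stands between an intolerance rule and a pointer to adverse events, whereas 5.3.1 is specific, mandatory and has no time limit, so it would ordinarily govern. This is the likelier intent, and it stands as a reason to rate the point low. It does not remove the conflict, because 11.8 neither says this nor refers to 5.3.1.

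It can also be argued that the literal reading proves too much, since it would forbid even the Month 3 adjustment. That does not hold. Section 6.4 attaches the regimen-based dose to initiation, and 6.5 then only has participants continue the drug. A dose set once and never changed is therefore a coherent reading.

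The safeguards are real. Creatine kinase, aldolase and liver tests are done at every visit (Appendix B), prescription drugs are recorded (5.6), and staff review results as they arrive (12.1). Section 11.10 stops drug for Grade 3 or 4 reactions including myalgia, for confirmed drug-related Grade 3 transaminase elevation, and when continuing is judged not in the participant's interest. Its clause on developing an exclusion criterion is discretionary; through exclusion 3 (other statin contraindications) it might arguably reach a dose above the label cap. These measures limit harm, but none sets a dose. The label itself (Appendix D, 5.1) says that creatine phosphokinase monitoring with interacting drugs may not prevent severe myopathy.

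It is also fair that many switches would be harmless. Half of the six modelled paths lower exposure. Efavirenz to rilpivirine leaves 80 mg, twice the Table 1 dose but within the labelled 10 to 80 mg range. Of the modelled paths, only a move to darunavir/ritonavir breaches the label cap.

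**Conclusion.** The conflict is real but minor. For a switch between permitted regimens after Month 3, the literal text of 11.8 keeps a dose that can be 4 or 2 times the one in Table 1, and no other section gives a route to re-dose.

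Three stronger inferences are not supported:
- A reader might infer that the protocol intends participants to stay on the higher dose. The context of 11.8 points to tolerability, and 5.3.1 can be read as following the current regimen.
- A reader might take 0.4 to 2 as a forecast of overdosed participants. Those counts rest on assumed switch rates and include switches in the safe direction; 5.8-fold is the highest of the six modelled paths. The documents support only an unknown, probably very small number.
- A reader might infer a weakness in the primary analysis. The stated power and the primary test do not depend on 11.8.

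The dose ratios of 4 and 2 come straight from the documents. The exposure multiples depend on dose proportionality and on carrying over ratios measured at 10 mg. No multiple is offered for atazanavir or elvitegravir, which have no drug-specific ratio, or for lopinavir/ritonavir, whose 488% in Table 1 has no entry in Appendix D Table 3.

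**What to change.** Replace the second sentence of 11.8 with:

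*No dose adjustment will be made for intolerance. If a change in antiretroviral regimen alters the atorvastatin dose required by Section 5.3.1/Table 1, atorvastatin will be re-dispensed at that dose (and held until then if the required dose is lower), or stopped if the new regimen is prohibited under Section 5.7.*

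Ask participants to tell the study team before any regimen change. That instruction, not the new wording, is what shortens the gap between visits.

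The rule applies only when the required dose changes, and drug is held only when the new dose is lower, so switches within a dose band do not interrupt the 9 months of treatment.

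The cost is two sentences by amendment and one instruction, with no new data collection. The downside is an occasional unscheduled dispensing or short interruption. Drug comes through the NIH pharmacy, visits from Month 0 are at the NIH Clinical Center, and some participants may live outside the local area.

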11.9 Pausing Rules for the Protocol

The study drugs are very commonly used medications with wide experience and ASA is also an over the counter medication. The study will be monitored by the study team and if an unusual number of SAEs or grade 3 or 4 events occur related to participation in the research, the study will be paused in consultation with the IRB until the events are better evaluated.

11.10 Stopping Rules for an Individual Subject/Cohort

A study subject will be discontinued from further Study Agent(s)/Intervention(s) administration for:

- Any clinical AE, laboratory abnormality, intercurrent illness, other medical condition or situation occurs such that continued participation in the study would not be in the best interest of the subject.
- Development of any exclusion criteria may be cause for discontinuation.
- Grade 3 or 4 adverse reactions to the study drug, including myalgia, abdominal pain, and nausea.
- Grade 3 elevation of hepatic transaminases that is confirmed by repeated testing and is considered related to study drug.
- New pregnancy (see Section [6.9](#)).
- Development of allergy or hypersensitivity to study drug.
- Request by participant to withdraw from study.
- Development of a medical condition that requires administration of the following prohibited concomittent medications:
 - Systemic corticosteroids
 - Daily NSAIDs

- Immunomodulating medication
- Subject is judged to be at risk of failing to adhere to the study provisions to such a degree that, in the opinion of the investigator, the integrity of the study results might become compromised.

For all subjects withdrawn from study, the PI will evaluate on an individual basis if it is in the best interest of the participant to be followed by the protocol team with follow-up visits that include safety laboratory tests.

11.11 Premature Withdrawal of a Subject

If a subject elects to withdraw, end of study evaluations will be performed at the time of their withdrawal. Leukapheresis and MR carotid imaging may be performed if the study participation is nearing completion.

